8. SENSITIVITY ANALYSES

Since the study cohort was 9 Caucasian men and 1 Caucasian woman and study was very small no statistical sensitivity analyses will be run. However, summary data may be presented for different patient variables to see if there were any trends.

9. RATIONALE FOR ANY DEVIATION FROM PRE-SPECIFIED ANALYSIS PLAN PERFORMED BY STIMDIA

Not applicable.

10. QC PLANS

The accuracy of the study data entered into the database will be 100% verified by Stimdia Medical quality and clinical personnel. Any data or statistical analyses will have a 100% second person verification.

11. PROGRAMMING PLANS

Synchrony will be measured by first finding when inspiration starts using the trigger flows for each subject/stimulation combination. Next the start of stimulation will be found using the trigger signal. The difference in time between the start of inspiration and the start of stimulation will be the lag time. This will be calculated for all stimulated breaths.

Work of Breath (WOB) is calculated by finding the end of stimulation using the trigger signal, waiting 100 msec, and then capturing the next 50 observations for WOB. Each set of 50 observations is summarized using the mode of the 50 observations. This is also done for each stimulated breath.

If the lag time is less than 88 msec, and the WOB is between 0.2 and 2.0 Joules/L, and the output parameter is less than 10.5 volts then capture will have been achieved and a binary indicator variable will be set to 1.0. If capture is not achieved, that binary indicator variable will be set to 0.0. This binary indicator variable will be used for analyzing the primary endpoint.

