4.2 Equipment and Accessories Used

The equipment used during the study may be divided in three categories:

1. **Stimulation System:** PEPNS Control system, used to stimulate the left and right phrenic nerve in concert with the inspired flow. This equipment, including the pacing leads, insertion kits and lead deployment device are provided by Stimdia.
2. **Data Acquisition:** PowerLab Data Acquisition System: used to log pressure, flow, WOB and Electrical Stimulation in experiments at 1000 Hz. This equipment, which is commercially available, is provided by Stimdia.

3. **Other Equipment:** Used to measure patient hemodynamics and vital signs during therapy as well as visualize and stimulate phrenic nerve during setup. This equipment is provided by clinical investigation site.

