5.2 Secondary Endpoints

Secondary Endpoints
1. The percentage of patients who receive safe and successful placement of the multipolar lead in the left and right phrenic nerve utilizing ultrasound guidance will be determined.
2. Phrenic nerve stimulation in synchrony with Mechanical Ventilation (MV) breaths will be measured to verify that occurs with inspiration.
3. The percentage of patients who experience one or more serious device/procedure-related adverse events during the study will be reported.

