In addition, there may be additional analyses conducted and other tables and graphs created for the final clinical study report based on the outcomes of the initial analyses and additional data points of interest.

An interim analysis may be run and this was allowed in the protocol. See Statistical Methodology section for greater details.

PRIMARY ENDPOINTS

The primary endpoints for the study relate to the ability of the therapy to mobilize the diaphragm and of the PEPNS system to stimulate specific levels of work of breathing.

- Capture of the Left and/or Right Phrenic Nerve > 80% with an output parameter of < 10.5 volts.
- WOB (Work of Breathing) kept between 0.2 Joules/L and 2 Joules/L for 80% of stimulated breaths.

The capture of the left and right phrenic nerve will be demonstrated during setup and by maintaining the WOB between 0.2 and 2 Joules/L. The stimulation voltage resultant from the tissue impedance and the user set current will be logged and evaluated to ensure it is less than 10.5 volts. Capture will also be evaluated in terms of synchrony.

The ability of the stimulation pulse to capture the diaphragm will be assessed using WOB (Work of Breathing Measurements). A logistic regression model with successful capture as the outcome will be used. The model will include repeated measurements within a subject.

Model:

$\text{capture} = (\text{timepoint}) (\text{subject})$

where subject is a random effect, and the outcome of capture is yes/no based on whether the stimulation captures the diaphragm.

Capture for this analysis is defined as synchrony of the stimulated breath with the output parameter < 10.5 volts and WOB between 0.2 and 2.0 Joules/L. Synchrony will be achieved if the lag time between start of inspiration and start of stimulation is less than 88 ms.

Hypothesis:

H_0 : The proportion of capture is less than or equal to the performance goal (PG) of 80%. Note: This hypothesis used a 90% performance goal in the protocol for the purposes of sample size calculation to ensure that there would be sufficient data to achieve the 80% performance goal when taking into account lost to follow up due to death, etc.

$H_0: \hat{p}_1 \leq \text{PG}$

H_A : The proportion of capture is greater than the performance goal of 80%.

$H_A: \hat{p}_1 > \text{PG}$,

where \hat{p}_1 is the estimated proportion of capture from the logistic model accounting for repeated measurements within a subject.

Sample Size:

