The percentage of patients who experience one or more serious device/procedure-related adverse events during the study will be reported. The evaluation results for the follow-up x-ray will also be noted.

Stim and Vent Synchrony

The phrenic nerve stimulation in synchrony with Mechanical Ventilation (MV) breaths will be measured to verify that it occurs with inspiration over all of the stimulated breaths for each of the patients. The synchrony on the detection of inspiration and expiration will be compared against the user set trigger flow section and compared to a fast trigger time which has been reported as 88 msecs.

Related Evaluations

Critical Care Pain Observation Tool (CPOT) assessments are made on all patients enrolled and will be reported before during and after stimulation on all patients. The pain assessment tool, CPOT, is based on four domains: the patient's facial expressions, body movements, compliance with ventilator (or voice use for non-intubated patients), and muscle tension. Each domain has a possible score of 0 to 2. The total score can vary between 0 and 8, where 0 indicates no pain behavior and 8 indicates clear signs of pain behavior.

Richmond Agitation and Sedation Scale (RASS) scores will be reported on all patients. The RASS measures agitation and sedation level, the score ranging from +4 to -5, where a score of 0 indicates an awake and adequate patient. Scores from -1 to -5 indicate an increasingly sedated patient, and scores from +1 to +4 indicate an increasingly irritable and agitated patient.

The CPOT and RASS scores will be evaluated to determine that the stimulation does not cause pain to the patient.

An assessment will be made to determine the sensitivity of the lead to patient position. Patient will be repositioned every 2 to 4hrs per hospital protocol and disease diagnosis requirements. Leads will be disconnected from the electrical stimulator using the extension lead during these non-stim periods. Reestablishing stimulation after reconnection will be evaluated along with the ability of the system to handle patient repositioning.

Vitals signs and blood gasses will be evaluated to determine if electrical stimulation does not have an untoward effect on patient. This will be evaluated by an expert in ICU ventilation / blood gas analysis.

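### The synchrony test looks only at when stimulation starts, so it cannot detect stimulation that runs past the end of inspiration

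*SAP*

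**What the plan says.** Protocol section 5.2 sets the aim of secondary endpoint 2: stimulation in synchrony with ventilator breaths "will be measured to verify that occurs with inspiration". SAP section 2 repeats it for all stimulated breaths in each patient. Under Stim and Vent Synchrony it adds: "The synchrony on the detection of inspiration and expiration will be compared against the user set trigger flow section". The same sentence brings in 88 ms as a reported fast trigger time.

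The rule itself appears twice. SAP section 2, Primary Endpoints: "Synchrony will be achieved if the lag time between start of inspiration and start of stimulation is less than 88 ms". SAP section 11: "The difference in time between the start of inspiration and the start of stimulation will be the lag time".

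The end of stimulation is also extracted in SAP section 11, but for another purpose. WOB is obtained by "finding the end of stimulation using the trigger signal, waiting 100 msec, and then capturing the next 50 observations for WOB", and those 50 values are summarised by their mode.

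The binary capture indicator, which is the outcome of the primary analysis, then combines three conditions: "If the lag time is less than 88 msec, and the WOB is between 0.2 and 2.0 Joules/L, and the output parameter" below 10.5 volts.

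**The concern.** Stimulation can be out of phase with inspiration at either end: it can start at the wrong moment, or it can stop too late. The SAP names expiration in its description of the synchrony analysis, yet the rule it programs addresses only the start. The 88 ms limit is a trigger-time benchmark, so it too concerns onset and has no counterpart for offset.

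At stake is what the synchrony percentage can be taken to show. A high figure would be read as evidence that stimulation occurred with inspiration. Under the rule as written it is evidence that stimulation began soon after inspiration began. The same lag condition is one of the three parts of the primary capture indicator, so the limitation carries over to that part of the primary endpoint.

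**Working it through.** The plan states no figure on this point, so there is none to reproduce. The check is a trace of the rule, then one illustration.

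**1. Inputs to the synchrony test.** Lag = start of stimulation − start of inspiration; pass if lag < 88 ms (SAP sections 2 and 11). Define offset d = end of stimulation − end of inspiration, so that d > 0 means overrun. The test contains no term in d. Two breaths with the same lag get the same result, one with d < 0 and the other with d > 0 of any length. The pass rate is therefore the same whether overrun occurs in no breath or in every breath.

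**2. Inputs to the capture indicator.** Capture = 1 if lag < 88 ms and WOB is 0.2 to 2.0 Joules/L and output is < 10.5 volts. Again there is no explicit term in d. WOB does depend on d indirectly, because its window is anchored to the end of stimulation. Protocol section 4.2 says the acquisition system is "used to log pressure, flow, WOB and Electrical Stimulation in experiments at 1000 Hz". If the 50 observations are consecutive samples at that rate, they span 50 / 1000 s = 50 ms, and the window runs from 100 to 150 ms after stimulation ends. Relative to the end of inspiration it runs from d + 100 to d + 150 ms.

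- The window lies wholly after the end of inspiration whenever d > −100 ms.
- That includes breaths with no overrun, where stimulation stops up to 100 ms before inspiration ends.
- So a WOB reading taken in exhalation does not by itself separate overrun from no overrun. The SAP does not say what the WOB signal reads there. An overrun breath may pass or fail on WOB.

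**3. Other places that might supply an offset check.**

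| Place | What it contributes |
|---|---|
| Protocol 6.14 (titled as the synchrony analysis) | Counts stimulated breaths with WOB inside control limits; no timing rule |
| SAP 2, Stim and Vent Synchrony | Names detection of expiration; no formula and no limit for stimulation end |
| SAP 11 | Programs onset lag only |

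None compares the end of stimulation with the end of inspiration.

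**4. Illustration for capture with an offset condition.** The documents give no overrun frequency, so let q be an assumed share of otherwise captured breaths that would fail on offset. Starting from the SAP's expected capture rate p = 97.5%, the rate with the condition is p × (1 − q):

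- q = 5%: 0.975 × 0.95 = 92.6%
- q = 10%: 0.975 × 0.90 = 87.8%
- q = 15%: 0.975 × 0.85 = 82.9%
- q = 20%: 0.975 × 0.80 = 78.0%

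The rate reaches the SAP's 80% performance goal at q = 1 − 0.80 / p. That is 17.9% for p = 97.5%, 15.8% for 95%, 11.1% for 90% and 5.9% for 85%. The test uses a lower confidence bound, so it would fail at a smaller q than these. The figures show how sensitive the result would be; they do not estimate what will be found.

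**The case against.** The strongest reply is that the documents nowhere show that overrun happens. The system has a flow sensor and is described as stimulating in step with the ventilator's inspiratory cycle (Protocol sections 2 and 4.1). The SAP speaks of detecting expiration, and the detailed operating instructions are in a manual outside these documents (Protocol section 7.1). If each train ends on detected expiration, overrun may be negligible. This stands as far as size is concerned. It does not answer the point about the rule, because an endpoint meant to verify timing should measure it rather than assume it.

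A reader might infer three stronger things that the documents do not support:

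- *Every overrun breath counts as captured.* Capture also requires WOB and voltage to pass, and the WOB window moves with the end of stimulation. Only the synchrony test is shown to be blind to overrun.
- *The plan ignores expiration.* SAP section 2 names an expiration-side comparison. What is missing is a calculation and a limit, and their inclusion in section 11.
- *The primary indicator must be redefined.* The SAP already lists patients P03 to P12 (Table 3) and describes a cohort of nine men and one woman (sections 7 and 8). Adding a failure condition to the primary outcome at that stage would need its own justification.

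It is also fair to say that Protocol section 6.14 judges effectiveness by WOB rather than by phase at both ends. But WOB within limits is not a measure of timing, and the stated endpoint is about timing.

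**Conclusion.** The concern holds for the synchrony test. The rule scores onset alone and cannot register stimulation that outlasts inspiration, although the endpoint is to verify that stimulation occurs with inspiration and SAP section 2 names both phases. This is a mismatch between two sections of the SAP and more than a missing detail, because the rule that is stated gives the same answer with or without the failure.

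For the primary endpoint the conclusion is conditional: an overrun breath is captured only if its WOB and voltage pass, and the documents do not settle how often that would be.

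The size is unknown. The 17.9% break-even rests on the SAP's expected 97.5% capture rate and on an assumed q. No stimulation or inspiratory durations are given from which q could be derived.

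**What to change.** Reconcile SAP section 2 (Stim and Vent Synchrony) with section 11:

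1. Locate the end of inspiration from the recorded wye flow, at the change to expiratory flow.
2. For every stimulated breath, compute end of stimulation minus end of inspiration.
3. For secondary endpoint 2, report per patient the distribution of this offset and the percentage of breaths that exceed a tolerance. State the tolerance and its basis before any offset is computed.
4. Leave the primary capture indicator unchanged. As a supporting analysis, present capture with and without the offset condition.

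The cost is a few lines of programming. Flow and stimulation are already logged at 1000 Hz and the end of stimulation is already extracted, so no new data or patients are needed. The sponsor has to choose and justify a tolerance. The downside is that the reported synchrony percentage may fall; if overrun is negligible, the added figure will show that in the device's favour.
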